8.4. Dose-limiting toxicity follow up period

The dose-limiting toxicity period is defined from the day of CD62L⁻ Tem infusion up to 72 day post infusion. **All** patients receiving the Tem-infusion are required to be followed for the full dose-limiting toxicity period.

Any patients experiencing the following adverse event during this time will be considered to have experienced a dose-limiting toxicity:

- Grade II-IV, acute-pattern Graft-versus-host disease (GvHD)

In the event of a DLT, UCL CTC should be contacted immediately and a **GvHD (DLT) Urgent Notification** CRF submitted within 24 hours see section 12 (Safety Reporting). The time of onset will be the date of the decision to treat or date of confirmatory biopsy whichever is earlier.

Rolling GvHD and GvHD assessment forms should be submitted to record the details of each incidence of GvHD (including those not meeting the definition of a DLT) and resubmitted if the grade/type of GvHD changes. These are non-urgent forms and can be posted as per section 11 (Data management and data handling Guidelines).

The severity of acute pattern GvHD is graded upon modified Glucksberg criteria as outlined below (16):

Stage	Skin	Liver (Bilirubin)	Upper GI ¹	Lower GI (diarrhoea output ³)
0	No active erythematous rash	<35 micromol/l	No symptoms	<500ml day or <3 episodes/day
1	Maculopapular rash <25% BSA	35 - 50 micromol/l	Persistent nausea, vomiting or anorexia ²	500-999ml/day or 3-4 episodes/day
2	Maculopapular rash 25-50% BSA	51-100 micromol/l		1000-1500ml/day or 5-7 episodes/day
3	Maculopapular rash >50% BSA	101-250 micromol/l		>1500ml/day or >7 episodes/day
4	Generalized erythroderma (>50% BSA) PLUS desquamation or bullae 5% > BSA	>250 micromol/l		Severe abdominal pain ± ileus or gross bloody stool (regardless of volume)

Individual target organ stage:

¹ Diagnosis of upper gut GVHD is based upon endoscopy and biopsy or clinical exclusion of other causes

² Nausea >2 days and vomiting >1 day or anorexia with weight loss

³ Assume volume per individual diarrhoea episode is 200ml

Overall GvHD Grade:

Grade 0: No stage 1-4 for any organ

Grade 1: Stage 1-2 skin without liver, upper GI, or lower GI involvement

Grade 2: Stage 3 skin and/or stage 1 liver and/or stage 1 upper GI and/or stage 1 lower GI **Grade 3:** Stage 2-3 liver and/or stage 2-3 lower GI, with stage 0-3 skin and/or stage 1 upper GI **Grade 4:** Stage 4 for skin and/or stage 4 liver and/or stage 4 lower GI, with stage 0-1 upper GI

8.5. Post-DLT Period Follow Up

After completing the Dose-Limiting Toxicity Follow Up Period (72 days post-Tem infusion), patients are followed up at days +100, +180, +270 and +360 post-stem cell transplant. Following the day +360 visit, the patient's status will be collected on an annual basis. See section 9 for assessment details.

8.6. Follow Up after Graft Failure, Progression or Relapse

Patients with graft failure or that progress or relapse **during** the dose-limiting toxicity period will be followed up for the full 72 day DLT Follow Up Period (as per sections 8.4 and 9.4). Upon completing the DLT Follow Up Period these patients will no longer be required to attend days +100, +180, +270 and +360 post-stem cell transplant visits. The patient's status will continue to be collected on an annual basis from their stem cell transplant date.

Patients with graft failure or that progress or relapse **after** the dose-limiting toxicity period will no longer be required to attend the relevant remaining days +100, +180, +270 and +360 post-stem cell transplant visits. The patient's status will continue to be collected on an annual basis from their stem cell transplant date.

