8.9. Supportive Care

Prevention and management of infection

All patients should receive standard anti-microbial and anti-viral prophylaxis according to local policy to prevent infection by Pneumocystis carinii, encapsulated bacteria and herpes or varicella zoster re-activation. All at risk patients should undergo regular monitoring for CMV, EBV and adenoviral infection by peripheral blood PCR with preemptive therapy commenced according to local policy. All new respiratory infections should be screened by respiratory viral screening and where relevant sputum culture or bronchiolar lavage. Use of anti-fungals drugs as primary treatment or secondary prophylaxis will be according to local policy.

Relapse or progression

In the event of relapse or progression at any time point, patients will be eligible to receive additional therapy. Suitable therapies might include unmanipulated donor lymphocyte infusion (DLI), therapeutic antibody, small molecular inhibitors, epigenetic modifying agents, chemo- or radiotherapy or any combination thereof, according to local policy. Patients that progress or relapse post-Tem infusion will continue to be followed up as per sections 9.4 and 9.5.

Mixed chimerism

Determination of chimerism will be performed at Great Ormond Street Hospital NHS Trust to ensure uniformity throughout the trial and will be performed by PCR-STR. These assays will be performed according to standard operating procedures of the Central Laboratory and subject to internal quality control and quality assurance. The Central Laboratory participates in an external quality assurance scheme (UK NEQAS). Any patient who subsequently develops a significant fall in donor chimerism (defined as <50% donor chimerism) will be eligible to receive unmanipulated DLI or any alternative treatment as decided by the PI at each centre.

Unmanipulated DLI

In accordance with standard UK practice, all registered patients will be eligible to receive unmanipulated DLI from 6 months post-transplant if investigations confirm persistent disease or mixed chimerism. From 6 months post-transplantation, the risk of unmanipulated DLI causing GvHD is low if given according to an escalated dose regimen. An example of a conventional escalated dose regimen of unmanipulated DLI is 1×10^6 , 3×10^6 , 1×10^7 , 3×10^7 and 1×10^8 CD3 cells/kg at 10 week intervals provided patients have no evidence of active GvHD or prior acute GvHD grade II-IV.

Management of acute and chronic GvHD

See section 7

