9.5. Assessments during Follow Up

The following investigations should be performed at days +100, +180, +270 and +360 post-stem cell transplant (+/- 10 days):

- Disease assessment as per local policy
- Adverse reaction assessment (including GvHD assessment)
- Physical examination & weight
- Full blood count with differential
- Biochemistry (sodium, potassium, urea, creatinine, calcium, phosphate, albumin, total protein, bilirubin, AST/ALT, alkaline phosphatase)
- Lymphocyte subset analysis (to include percentages and absolute numbers of CD3 T cells, CD4 T cells, CD8 T cells, B cells and NK cells); *N.B. this sample must be taken on the same day as the central lab samples below.*
- Peripheral blood samples for central labs:
 - 25ml in lithium heparin Viral and antigen-specific immunity & immune reconstitution
 - 10ml in EDTA chimerism analysis

The following samples should also be taken at days +100 and +360 post-stem cell transplant (+/- 10 days):

- Peripheral blood samples for central labs:
 - 10ml in EDTA TCR analysis

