9.6. Assessments during Long Term Follow Up

After the patient has completed the initial 360 days post-stem cell transplant follow up, or following progression, the following information should be collected annually (+/- 28 days):

• Patient status (including disease status)

Please note that the annual follow up for all patients is based on the stem cell transplant date, e.g. 1 year post-transplant, 2 years post-transplant, etc.

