12.5.1. Reporting of Infections Requiring Inpatient Admission

Details of infections requiring inpatient admission from the date of CD62L⁻ Tem infusion to 360 days post stem cell transplant must be reported on the Infection rolling form. The infection rolling form is to be submitted to UCL CTC with each scheduled trial visit (if no infections requiring inpatient admission occurred, only the cover sheet needs to be submitted).

For the purposes of the ToTem trial, infections requiring admission to hospital (**unless considered to be related to the investigational treatment)** do not need to be reported on the trial SAE report form. If the infection is fatal, life-threatening, prolongs an existing hospitalisation or meets any other seriousness criteria an SAE report must be submitted as per section 12.2.2.

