17.2.2. Analysis of secondary endpoints and secondary analyses

Incidence and severity of acute GvHD (whether dose-limiting or not)

Incidence and severity of acute GvHD (dose-limiting or not), as defined by the Glucksberg Scale, will be reported per dose level in frequency tables.

Incidence and severity of chronic GvHD

Incidence and severity of chronic GvHD will be reported per dose level in frequency tables.

Non-relapse mortality at 1 year

Non-relapse mortality (NRM) is defined as the time from registration to time of death without relapse. NRM will be presented using a Kaplan-Meier (KM) plot (grouped across dose level and per dose level), and 1-year NRM rate will be estimated (with 95% confidence intervals).

Overall- and Event-free survival at 1 year

Overall survival (OS) is defined as the time from registration to time of death from any cause. Event-free Survival (EFS) is defined as time from registration to the occurrence of any of the following events: graft failure, disease relapse, disease progression, or time of death from any cause. OS and EFS will be presented using KM plots (grouped across dose level and per dose level), and 1-year OS and EFS rates will be estimated (with 95% confidence intervals).

Incidence/type of infection requiring inpatient admission at 1 year

Infections that require inpatient admissions from date of Tem Infusion until +360 days post-stem cell transplant will be documented, and the type of infection and duration of inpatient stays will be reported per dose level.

Total Number of inpatient days at 1 year

The median and range for the total number of days that patients spend in hospital as inpatients from the date of Tem Infusion up to 1 year post allo-SCT will be reported.

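### Sections 8.6 and 9.6 conflict with 8.9 on follow-up after relapse or progression, so GvHD, infection-admission and inpatient-day data to 1 year can be incomplete

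*Protocol*

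**What the plan says.** Three sections of the protocol set follow-up after a relapse-type event.

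- **8.6** covers graft failure, progression and relapse. If the event falls within the DLT period, the full 72 days are completed and the later visits are dropped. If it falls afterwards, the patient "will no longer be required to attend the relevant remaining days +100, +180, +270 and +360 post-stem cell transplant visits". In both cases only status is collected, each year from the transplant date.
- **9.6** puts patients on the annual schedule once day 360 is complete "or following progression, the following information should be collected annually". The only item listed is patient status, including disease status.
- **8.9**, under relapse or progression, says: "Patients that progress or relapse post-Tem infusion will continue to be followed up as per sections 9.4 and 9.5". Section 9.5 consists of the day +100, +180, +270 and +360 assessments.

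The reporting sections use calendar windows. Sections 12.4 and 12.5.1 ask for all GvHD and all infection admissions from infusion to 360 days after transplant, and the table in 12.8 repeats this. None makes an exception for relapse. Submission, however, is tied to visits: "The infection rolling form is to be submitted to UCL CTC with each scheduled trial visit". Section 12.4 has the same arrangement for the GvHD rolling form.

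Section 17.2.2 reports infection admissions to day 360 by dose level, chronic GvHD in frequency tables, and, for hospital stay over the first year after transplant, "The median and range for the total number of days that patients spend in hospital as inpatients from the date of Tem Infusion".

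**The concern.** A site whose patient relapses on day 120 has two instructions that cannot both be carried out: stop the remaining visits, or keep them. If it stops them, the duty to record GvHD and infection admissions to day 360 remains, but no scheduled visit is left at which to send the forms. For total inpatient days the position is weaker still. The 9.5 and 9.6 lists and the 12.8 table name no item or form for them, and annual status does not supply them.

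An analysis plan cannot repair this, because the conflict decides which data exist. At stake is the completeness of three secondary endpoints. Two of them, infection admissions and inpatient days, bear directly on the benefit described in the background: fewer infection-related deaths, fewer readmissions and shorter stays. With at most 18 patients, divided among dose levels, a few incomplete records can alter a table.

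**Working it through.** **Step 1. The sections side by side**

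| Section | Who | Day +100 to +360 visits | What is collected |
|---|---|---|---|
| 8.6 | Graft failure, progression, relapse | Not required | Annual status |
| 9.6 | Progression | Replaced by annual collection | Patient and disease status |
| 8.9 with 9.5 | Progression, relapse | Continue | Full 9.5 list, including GvHD assessment |
| 12.4, 12.5.1, 12.8 | All infused patients | Assumed to occur | GvHD and infection admissions to day 360 |

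For progression, 8.9 contradicts both 8.6 and 9.6. For relapse it contradicts 8.6. Graft failure is named only in 8.6, so nothing contradicts the visit rule there, but the reporting windows in 12.4 and 12.5.1 still apply to those patients.

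**Step 2. Is there another route for the data?** In part. Under 12.8, an infection that is serious for a reason other than admission, or an admission judged related to the infusion, goes on an SAE report until the end of the trial. So does serious GvHD judged related. Under 12.2.2, other serious events more than 72 days after infusion are exempt. That leaves without a scheduled route: unrelated infection admissions with no other seriousness criterion, non-serious GvHD, and inpatient days in general. The first annual contact falls at about day 365 ± 28, that is day 337 to 393, but its listed content is status only.

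**Step 3. Length of the exposed window**

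Inputs: infusion on day 24 to 32 (8.2.3), DLT period of 72 days (8.4), reporting to day 360 (12.4, 12.5.1).

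- Reporting window = 360 − infusion day: 360 − 24 = 336; 360 − 32 = 328 days.
- End of DLT period = infusion day + 72: day 96 to day 104.
- Days after that point = 360 − 96 = 264; 360 − 104 = 256.
- Share = 264/336 = 78.6%; 256/328 = 78.0%.

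For a relapse on day 120 with infusion on day 28, the window is 332 days and 360 − 120 = 240 days (72%) follow the relapse. The last scheduled visit was day +100, so 360 − 100 = 260 days (78%) follow the last scheduled submission.

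**Step 4. How far the summaries could move.** The protocol gives no relapse or admission rates, so the following figures are assumptions: 18 patients, one infection admission per patient-year, mean stay 10 days, infusion on day 28, relapse spread evenly from the end of the DLT period to day 360. The simulation takes the extreme case in which all recording ends at relapse, and it ignores death.

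| Patients relapsing | Mean of trial median inpatient days: stopped vs kept | Patients with an infection admission: stopped vs kept |
|---|---|---|
| 10% | 6.3 vs 6.9 | 58% vs 60% |
| 30% | 5.1 vs 6.9 | 54% vs 60% |
| 50% | 4.0 vs 6.9 | 50% vs 60% |
| 30%, admission rate doubled after relapse | 5.1 vs 8.0 | 54% vs 63% |

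Because 12.4 and 12.5.1 still ask for GvHD and infection admissions to be recorded, these gaps mark the outer end of what could happen on these assumptions, not a forecast.

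**The case against.** The strongest reply is that the recording duties are set by date and not by visit. Sections 12.4, 12.5.1 and 12.8 run to day 360 without exception, so a careful site would still report GvHD and infection admissions after relapse, and the visit only fixes when the form is sent. This stands. It rules out the claim that collection simply stops under 8.6. What remains is a duty with no scheduled point of submission, and no named item for inpatient days.

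A reader might go further and infer that poor outcomes flatter the results, because a patient who dies or relapses early accrues few inpatient days. The documents do not support that. Shorter observation caps the count, but sicker patients may be admitted more beforehand. With infusion on day 28, a patient who dies on day 60 could contribute up to 60 − 28 = 32 days, well above the illustrative median of about 7. The net direction is unknown.

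A reader might also treat the median and range of totals as an error in itself. How a descriptive total handles death or incomplete follow-up may properly sit in the analysis plan, which is not at hand, and survival and non-relapse mortality are reported alongside.

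Two further points stand. After relapse, patients may receive other therapy, including unmanipulated donor lymphocytes (8.9), so later GvHD and infections are harder to attribute, and ending collection at relapse would be defensible if the protocol said so consistently. And the trial's main decision is protected, because 8.6 keeps the full 72 days. The version history lists 8.6 and 9.6 as added in version 2.0, so the sentence in 8.9 may be older text. That may explain the conflict but does not remove it.

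**Conclusion.** The inconsistency is certain from the text: 8.6 and 9.6 cannot be followed together with 8.9 and 9.5, and 12.4, 12.5.1 and 12.8 rely on visits that 8.6 removes. The consequence is conditional. If sites apply 8.6 and 9.6, GvHD, infection admissions and inpatient days can be incompletely and inconsistently collected after relapse, progression or graft failure, over as much as 78% to 79% of the infusion-to-day-360 window for a patient whose visits end with the DLT period.

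How many patients this would affect cannot be derived from the protocol. At an assumed 20% to 40% with such an event by 1 year, 18 × 0.2 = 3.6 to 18 × 0.4 = 7.2, or about 4 to 7 patients. No direction of bias is established. The primary DLT endpoint, and therefore the dose recommendation that rests on it, is not affected. The point is worth correcting because named secondary endpoints depend on it.

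**What to change.** Reconcile 8.6, 8.9, 9.6, 12.4 and 12.5.1 so that they give one rule for relapse, progression and graft failure alike. State that GvHD, infection admissions and inpatient admission and discharge dates are collected from hospital notes to day 360 after any of these events, with no trial visit needed, and name the time by which the forms are due. Section 15.2.1 already has such a route for patients who stop trial visits but allow data collection: forms are completed from the routine visit nearest the due date.

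Flag events after relapse as such, so that they can be read apart from those possibly due to later therapy. In the infection and inpatient-day summaries of 17.2.2, show each patient's observed time, ending at death, end of follow-up or day 360. No new endpoint is needed.

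The cost is a wording amendment and a small amount of note-based data entry for the patients concerned, with no added visits or procedures.

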8.7. Management of Adverse Events

Patients with acute pattern or chronic GvHD should be treated according to local policies. For patients developing acute-pattern GvHD grade II-IV, a standard treatment involves systemic methylprednisolone at a dose of 1-2mg/kg intravenously followed by a taper and switch to oral prednisolone according to response. Such patients are usually maintained or re-started on a calcineurin inhibitor with the aim of achieving therapeutic levels. Subsequent taper of immunosuppression is according to clinical response. Patients failing to respond to such therapy should be managed according to local practice.

For patients who develop moderate-severe chronic GvHD, a combination of cyclosporine/ prednisolone is also a standard therapy. Alternative or additional therapies may be initiated in patients who fail to respond or who are steroid-dependent or who are intolerant of this treatment according to local practice.

Where patients develop corticosteroid treatment-refractory acute grade II-IV GvHD or moderate-severe chronic GvHD, they will be eligible to enter other clinical trials if appropriate.

8.8. Management of Investigational Treatment Error, or Occupational Exposure

Investigational treatment error

An investigational treatment error is any unintentional error in prescribing, dispensing, or administration of an investigational treatment while in the control of a healthcare professional or consumer. The error can be identified either by the trial team at site or by the Sponsor upon review.

Investigational treatment errors should be reported on in incident report (see section 13.1). Any adverse events resulting from an investigational treatment error should be reported as an SAE (see section 12.2.2 for reporting procedures).

Occupational exposure

Exposure to an investigational treatment as a result of one's professional or nonprofessional occupation. Occupational exposure should be reported on an incident report form (see section 13.1).

8.9. Supportive Care

Prevention and management of infection

All patients should receive standard anti-microbial and anti-viral prophylaxis according to local policy to prevent infection by Pneumocystis carinii, encapsulated bacteria and herpes or varicella zoster re-activation. All at risk patients should undergo regular monitoring for CMV, EBV and adenoviral infection by peripheral blood PCR with preemptive therapy commenced according to local policy. All new respiratory infections should be screened by respiratory viral screening and where relevant sputum culture or bronchiolar lavage. Use of anti-fungals drugs as primary treatment or secondary prophylaxis will be according to local policy.

Relapse or progression

In the event of relapse or progression at any time point, patients will be eligible to receive additional therapy. Suitable therapies might include unmanipulated donor lymphocyte infusion (DLI), therapeutic antibody, small molecular inhibitors, epigenetic modifying agents, chemo- or radiotherapy or any combination thereof, according to local policy. Patients that progress or relapse post-Tem infusion will continue to be followed up as per sections 9.4 and 9.5.

Mixed chimerism

Determination of chimerism will be performed at Great Ormond Street Hospital NHS Trust to ensure uniformity throughout the trial and will be performed by PCR-STR. These assays will be performed according to standard operating procedures of the Central Laboratory and subject to internal quality control and quality assurance. The Central Laboratory participates in an external quality assurance scheme (UK NEQAS). Any patient who subsequently develops a significant fall in donor chimerism (defined as <50% donor chimerism) will be eligible to receive unmanipulated DLI or any alternative treatment as decided by the PI at each centre.

Unmanipulated DLI

In accordance with standard UK practice, all registered patients will be eligible to receive unmanipulated DLI from 6 months post-transplant if investigations confirm persistent disease or mixed chimerism. From 6 months post-transplantation, the risk of unmanipulated DLI causing GvHD is low if given according to an escalated dose regimen. An example of a conventional escalated dose regimen of unmanipulated DLI is 1×10^6 , 3×10^6 , 1×10^7 , 3×10^7 and 1×10^8 CD3 cells/kg at 10 week intervals provided patients have no evidence of active GvHD or prior acute GvHD grade II-IV.

Management of acute and chronic GvHD

See section 7

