
8.10. Contraindications

Patients are not permitted to receive any other cellular therapy from the time of informed consent up to 72 days post CD62L⁻ Tem infusion. Patients will not be permitted to enter additional trials involving cellular therapies, ATIMP or IMPs **UNLESS** they develop corticosteroid treatment-refractory acute grade II-IV GvHD or moderate-severe chronic GvHD, where they will be eligible to enter other clinical trials if appropriate.

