17.2. Statistical Analysis

17.2.1. Analysis of main endpoint

Occurrence of dose-limiting toxicity (DLT, defined as acute-pattern GvHD grade II-IV)

For DLT analysis, all patients deemed eligible for toxicity assessment will form the analysis population. Incidence of DLT per dose will be described in tables. GvHD data will be used to provide final estimates of DLT risks and their uncertainty using the dose-toxicity model. These estimates, along with SRC recommendations, will determine the MTD and thus RP2D of Tem.

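### Sections 8.9 and 8.10 are not reconciled on donor lymphocyte infusion (DLI) during the DLT window, and the GvHD tables by Tem dose do not separate cases arising after DLI

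*Protocol*

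**What the plan says.** Section 8.9 (Supportive Care) has three paragraphs that bear on DLI.

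- **Relapse or progression:** "In the event of relapse or progression at any time point, patients will be eligible to receive additional therapy", followed by "Suitable therapies might include unmanipulated donor lymphocyte infusion (DLI), therapeutic antibody, small molecular inhibitors" and other options according to local policy.
- **Mixed chimerism:** a patient whose donor chimerism falls below 50% "will be eligible to receive unmanipulated DLI or any alternative treatment as decided by the PI at each centre". This paragraph sets no time limit.
- **Unmanipulated DLI:** "all registered patients will be eligible to receive unmanipulated DLI from 6 months post-transplant", on condition that persistent disease or mixed chimerism is confirmed.

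Section 8.10 (Contraindications) says: "Patients are not permitted to receive any other cellular therapy from the time of informed consent up to 72 days post" Tem infusion. Its only exception concerns entry into other trials for refractory acute or moderate-severe chronic GvHD.

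Section 8.4 defines the DLT as grade II-IV acute-pattern GvHD between infusion and 72 days: "Any patients experiencing the following adverse event during this time will be considered to have experienced a dose-limiting toxicity". It has no attribution test and no provision for an intervening cell product. Section 8.6 keeps patients who relapse in the window under DLT follow-up for all 72 days. Section 17.2.1 says "all patients deemed eligible for toxicity assessment will form the analysis population".

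Section 12.4 collects all GvHD from Tem infusion to day 360 after transplant. Section 17.2.2 tabulates acute and chronic GvHD per dose level, with no split at DLI.

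**The concern.** Two routes could credit GvHD caused by DLI to Tem.

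1. **DLT route.** A site that follows 8.9 without regard to 8.10 could give DLI for an early relapse while the patient is still under DLT follow-up. Grade II-IV acute-pattern GvHD after that DLI meets 8.4 and enters the dose-toxicity model as a Tem event. The same holds if 8.10 governs and the DLI is a deviation. The alternative is a decision to set the patient aside once the outcome is known, through the Safety Review Committee's (SRC) DLT evaluation (14.4.5) or the words on eligibility for toxicity assessment in 17.2.1. Handling settled after the outcome can bias the MTD.

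2. **Table route.** This does not depend on the conflict. DLI from 6 months is permitted, GvHD is collected to day 360, and the tables are by Tem dose alone. A reader of those tables could not tell which product preceded the GvHD.

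**Working it through.** **Timing.** Tem is infused on day +24 to +32, so the 72-day window closes between day 24 + 72 = 96 and day 32 + 72 = 104. Permitted DLI from 6 months starts at about day 180, after the window and before GvHD collection ends at day 360. With the 10-week intervals of the example regimen in 8.9, and a first dose at about day 180, doses fall near days 180, 250, 320 and 390. The first three (1x10^6, 3x10^6 and 1x10^7 CD3/kg) fall within the collection period. The Tem doses are 1x10^5 to 3x10^6/kg, so the two cell doses overlap.

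**Reproducing Table 1 (17.1).** The model is logit p = a + exp(b) × ln(dose / 3x10^6), with a ~ N(-1.39, variance 2.60) and b ~ N(-1.17, variance 0.22). The dose coding is inferred because it returns the table.

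- At the prior means, p for levels 1 to 4 is 8.0 / 10.9 / 15.0 / 19.9%. The protocol states 8 / 11 / 15 / 20%.
- Grid integration gives 90% intervals of 0.4-55.6, 0.7-63.0, 1.2-71.1 and 1.7-77.9%. The protocol states (0, 56), (1, 63), (1, 71) and (2, 78).

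The stated prior is reproduced.

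**Effect of one extra DLT.** The likelihood is binomial with complete 72-day follow-up. The indicated level is the one with posterior median closest to 20%, as in 17.1.

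| Data | Posterior medians, levels 1-4 (%) | Closest to 20% |
|---|---|---|
| 0/2 at level 3 | 3.9 / 5.6 / 8.3 / 11.8 | 4 |
| 1/2 at level 3 | 16.6 / 22.2 / 29.8 / 38.1 | 2 |
| 0/2 at level 3, 0/2 at level 4 | 2.7 / 3.9 / 5.8 / 8.3 | 4 |
| 0/2 at level 3, 1/2 at level 4 | 8.4 / 11.9 / 17.1 / 23.5 | 3 |
| 0/2 at level 3, 0/6 at level 4 | 1.8 / 2.6 / 3.9 / 5.6 | 4 |
| 0/2 at level 3, 1/6 at level 4 | 4.6 / 6.6 / 9.7 / 13.7 | 4 |

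Under the wording in 8.3 (estimated risk no more than 20%), the second row indicates level 1. In the last row the level stays at 4, but the early-stop rule requiring no DLTs can no longer be met.

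With 18 patients (0/2 at level 3 and 16 at level 4), 1, 2 or 3 DLTs at level 4 give 7.2, 11.7 or 16.6% there, and level 4 remains indicated each time. The level is not always stable later. With 1/4 at level 3 and 8 patients at level 4, going from 1 to 2 DLTs at level 4 raises that level from 17.4% to 24.8%. Level 3 is then at 18.6% and becomes the closest.

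**Frequency.** The documents give no rate for an in-window DLI followed by grade II-IV GvHD. If the per-patient probability q is assumed, the chance of at least one case in 18 is 1 - (1 - q)^18:

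- q = 1%: 16.5%
- q = 2%: 30.5%
- q = 5%: 60.3%
- q = 10%: 85.0%

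These values of q are assumptions that show a range. They are not estimates.

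**Table route.** Sections 8.9, 12.4 and 17.2.2 together give permitted DLI from about day 180, GvHD recorded to day 360, and frequency tables by Tem dose only. It is clearest for DLI given for persistent disease or mixed chimerism. After relapse, 8.6 ends the day +100 to +360 visits while 8.9 continues follow-up under 9.4 and 9.5, so capture of late GvHD in those patients is itself unclear.

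**The case against.** The strongest reply is that 8.9 and 8.10 can be read together. The phrase on timing in 8.9 qualifies the relapse, and DLI is one of several therapies that might follow. Section 8.10 is specific and unconditional, so non-cellular options would apply in the window and DLI afterwards. On that reading the defect is a missing cross-reference. This largely stands, but the text does not say it, and 8.4 would still score the GvHD if a DLI were given.

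The in-window chain is also long: no relapse at the pre-infusion check, then relapse, DLI against 8.10, and grade II-IV GvHD, all within 72 days. The chimerism route is nearly closed, because the first scheduled post-transplant sample is at day +100 (±10) and the window ends by day 104. This stands.

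Counting all grade II-IV acute-pattern GvHD regardless of cause is a defensible conservative rule, and 8.6 keeps relapsed patients under observation on purpose. Ending DLT follow-up at DLI in the main analysis could discard genuine late Tem GvHD. This stands too, which is why such a cut-off belongs in a sensitivity fit. Defining eligibility for toxicity assessment can, taken alone, be left to the SAP.

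On the tables, DLI from 6 months is conditional, 8.9 describes its GvHD risk as low under an escalated regimen, and the secondary tables do not set the MTD. That limits the consequence but does not remove the mixing.

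A reader might infer that DLI is simply allowed at any time, or that with 18 patients any single misattributed DLT changes the recommended level. The documents do not support either: 8.10 forbids the first, and the stated model contradicts the second in several of the configurations above.

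**Conclusion.** The point holds, at minor to moderate severity. Sections 8.9 and 8.10 need reconciling, because a site following 8.9 alone could give DLI in the DLT window and 8.4 with 8.6 would then count resulting grade II-IV acute-pattern GvHD against Tem. The event is unlikely and its rate is undocumented. Its effect is greatest in the first cohort (level-3 median 8.3% versus 29.8%, closest level 4 versus 2) and often disappears later, though not in every configuration. That early shift is an interim input to the SRC and not the final MTD.

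The mixing of two cell products in the GvHD tables needs no conflict and no deviation; it follows from the permitted schedule. It affects the interpretation of secondary endpoints only.

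The figures rest on the stated prior, the inferred dose coding that reproduces Table 1, and complete follow-up. An SAP, not seen here, may already separate post-DLI GvHD. The protocol does not.

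**What to change.** 1. Reconcile 8.9 with 8.10 on other cellular therapy before 72 days post Tem, with a cross-reference. Which rule holds is for the clinicians.
2. Record on the CRF the date of any DLI or other cellular therapy.
3. In 17.2.2, report acute and chronic GvHD per Tem dose up to first DLI, and list post-DLI GvHD separately.
4. In 8.4 and 17.2.1, state in advance how GvHD after an intervening cellular therapy in the window enters the model. Keeping the all-cause rule for the main fit is acceptable. Add a sensitivity fit that stops DLT follow-up at that therapy, so that handling is not decided case by case once the outcome is known.

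The cost is a few lines of protocol wording, one extra CRF date, one further model fit if a case occurs, and slightly longer reporting. The sample size and the escalation scheme are unaffected.
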